Hypothesis 1b: Participants who remit with IPT or combination treatment will have fewer relapses over follow-up than those who remit with fluoxetine.

Aim 2:

Investigate key presumed mediators of the relationship between treatment and remission

Hypothesis 2a: For initial treatment with IPT, change in social support will mediate the relationship between treatment and remission—improved social support will be associated with remission

Hypothesis 2b: For initial treatment with fluoxetine, change in emotional reactivity will mediate the relationship between treatment and remission—decreased emotional reactivity will be associated with remission.

Aim 3: Identify demographic and clinical moderators of the relationship between treatment and remission.

Hypothesis 3a: Time or cost for transport between participants' residences and KCH, and other Kisumu County Ministry of Health facilities will moderate the relationship between treatment and remission—higher time/cost will decrease the effect of initial treatment with IPT relative to fluoxetine (more treatment visits required for IPT versus fluoxetine treatment).

Hypothesis 3b: Severity of MDD and/or PTSD symptoms among non-remitters will moderate the relationship between subsequent treatment and remission, such that higher severity will decrease the effect of treatment on remission for treatment switch relative to treatment combination.

Hypothesis 3c: Q learning will produce personalized treatment algorithms using the above or other moderators.

Aim 4. Estimate the costs and cost-benefit ratios for fluoxetine and IPT treatment of depression and PTSD.

Hypothesis 4a: Pooled cost-benefit ratios will show that depression and/or PTSD treatment leads to net economic gain for individuals and households at month 6;

Hypothesis 4b: Separate analyses will find that IPT has a more favorable cost-benefit than fluoxetine at month 30.

Aim 5. Determine the acceptability and feasibility of delivering SMART-DAPPER treatments by telephone.

Hypothesis 5a. Telephone IPT will be acceptable and feasible.

Hypothesis 5b. Telephone fluoxetine provider appointments will be acceptable and feasible.

Aim 6. Determine the effect of telephone treatment delivery on retention in care.

Hypothesis 6a. Participants who elect to receive telephone treatment will have higher retention in care than those who receive face-to-face care.

Significance

The results of the proposed research will be significant in two ways:

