Study visits: To characterize the trajectory of symptom change during treatment, participants will be re-evaluated at the mid-point of treatment (month 1.5 for IPT and month 3 for fluoxetine). Treatment mid-point data is valuable because it can inform the minimum duration of treatment necessary to optimize mental health gains in a setting of scarce mental health resources. For example, if 90% of all observed treatment gains are achieved in the first half of treatment, subsequent implementation efforts might consider shortened courses of treatment. Participants will be assessed at month 3 (end of IPT treatment, mid-point of fluoxetine treatment) and at month 6 (end of fluoxetine treatment). For those participants who are in remission from depression and/or PTSD, follow up assessments will then continue at 9 month, 12 month and then at six month intervals until month 30 to assess for maintenance of gains and relapse. Assessments may be done at the health facility or by telephone. We are defining remission as absence of disease as defined by threshold criteria for Diagnostic and Statistical Manual of Mental Disorders-V (DSM-V) for PTSD and MDD. Those participants who have not yet remitted will be re-randomized to: switch of treatment (from IPT to fluoxetine or vice versa) or combination treatment (addition of IPT to fluoxetine or vice versa). See Figure 3.

Assessment schedule and rationale:

In order to characterize the trajectory of symptom change during treatment, participants will be re-evaluated at the mid-point of treatment (month 1.5 for IPT and month 3 for fluoxetine). Treatment mid-point data is valuable because it can inform the minimum duration of treatment necessary to optimize mental health gains in a setting of scarce mental health resources. For example, if 90% of all observed treatment gains are achieved by month 1.5, subsequent implementation efforts might consider shortened courses of treatment. Participants will be assessed at end of treatment (month 3 for IPT and month 6 for fluoxetine) and fluoxetine recipients will be tapered off the medication. At six months, participants will be re-assessed and then monitored at 6-month intervals until month 30 (Figure 3). Assessment visits may be done at the health facility or over the telephone.

Measures (Table 1): *Demographics.* We will obtain usual demographic measures, education, including individual income, assets, education and school fees, healthcare utilization, and time allocation.

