As identified by RDoC, current mental disorder disease categories may allow for diversity among psychological constructs of negative/positive valence, cognition, social processes and arousal/regulatory systems, undermining the utility of current disease definitions and average treatment responses for some individuals. Based on this concern, we will evaluate for heterogeneity in treatment response trajectories for individuals with MDD and/or PTSD using χ^2 tests (binary outcome, [threshold for DSM-V for MDD yes/no; PCL yes/no]) and t tests (continuous outcome, [depression symptoms, BDI/PTSD Symptoms PCL]) on key study outcomes. Next, we will use mixed-mode latent regression modeling to identify heterogeneous sub-group trajectories.(Haviland & Nagin, 2005) We will use the Bayes Information Criterion to identify the appropriate number of subgroups, deriving the smaller number.(Raftery, 1995)

Procedures and measurements to assess implementation approach (EPIS) and outcomes.

EPIS strategy. The feasibility, acceptability and utility of this study's EPIS strategy, including its use of a DAP to integrate the feedback from the implementation resource team (IRT) members into the delivery of evidence based depression treatment will be evaluated using semi-structured individual interviews and focus groups with inner and outer context IRT members, providers and study participants. Domains of interest. *IRT members* will be asked: (1) to identify positive and negative aspects of the EPIS model, IRT and DAP strategies, including content and process; (2) to identify ways to improve the DAP process. *Providers* (mental health and primary care) will be asked: (1) their awareness and understanding of the use of the EPIS model; (2) satisfaction or dissatisfaction with the EPIS, IRT and DAP strategies for adaptation of evidence-based

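### The first-step chi-squared and t tests cannot show heterogeneity of treatment response, and the latent trajectory step that follows has no stated visit window

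*Protocol*

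**What the plan says.** The relevant paragraph is in the protocol's Data analysis plan, after the paragraph on Hypotheses 1a and 1b. It starts from the worry that diagnostic categories and average responses may not describe some individuals. It then says the trial will "evaluate for heterogeneity in treatment response trajectories for individuals with MDD and/or PTSD using" chi-squared "tests (binary outcome, [threshold for DSM-V for MDD yes/no; PCL yes/no", and "t tests (continuous outcome, [depression symptoms, BDI/PTSD Symptoms PCL]) on key study outcomes". It gives no comparison groups, time point or interaction term.

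A second step follows: "Next, we will use mixed-mode latent regression modeling to identify heterogeneous sub-group trajectories". The number of classes is to be chosen this way: "We will use the Bayes Information Criterion to identify the appropriate number of subgroups, deriving the smaller number". The paragraph does not say which visits enter this model, or whether it depends on the result of the first step.

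Three other places matter:

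- Under Hypothesis and Specific Aims, Aim 3 is to "Identify demographic and clinical moderators of the relationship between treatment and remission", with Q-learning as Hypothesis 3c. The Data analysis plan gives no model for Aim 3.
- Under Study visits: "Those participants who have not yet remitted will be re-randomized to: switch of treatment (from IPT to fluoxetine or vice versa) or combination treatment".
- The SAP has no heterogeneity analysis. Its time-by-group interaction is an average contrast between arms.

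**The concern.** The question is whether the average response hides people who respond differently. A chi-squared or t test compares one proportion or one mean between two groups. It uses no repeated measures, so it does not test a trajectory. It has no interaction term, so it does not test whether a treatment effect varies.

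A significant result could be reported as heterogeneity when everyone benefits equally. A null result could be reported as homogeneity when benefits in one subgroup offset harms in another.

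The latent step raises a separate issue. If its visits extend beyond first-line treatment, some of the separation between classes may come from the second-line treatment assigned and not from differing response to the first.

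**Working it through.** The documents give no sample size, power or error rate for this step, so there is no stated figure to reproduce.

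**Inputs.**
- Total of 2710 (Sample size calculations), with arms of about equal size (Randomization and blinding): 2710 / 2 = 1355 per arm.
- Planned drop-out of 40%: 1355 × 0.6 = 813.
- The planned second-stage arm size of 242, used as a low value.
- Two-sided alpha of 0.05, borrowed from the sample-size section.
- All effect patterns below are assumptions. Each simulation cell has 2,000 runs, with two equal subgroups.

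**Reading A: the tests compare arms.**

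*Offsetting effects*, +0.5 SD in one half and −0.5 SD in the other, with remission of 65% and 35% against 50%:
- average effect = 0.5 × 0.5 + 0.5 × (−0.5) = 0
- average remission = 0.5 × 65% + 0.5 × 35% = 50%, equal to the comparator, so neither test has anything to detect.

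*Uniform effect*, 0.25 SD, or 60% against 50%. Power of the t test is approximately Φ(δ√(n/2) − 1.96):
- n = 242: 0.25 × √121 = 2.75, and Φ(0.79) = 0.785
- n = 813: 0.25 × 20.16 = 5.04, and Φ(3.08) = 0.999

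Simulated rejection rates (%):

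| Pattern | n per arm | t, arms | chi-squared, arms | interaction, continuous | interaction, binary |
|---|---|---|---|---|---|
| Offsetting | 242 | 5.0 | 5.9 | 100 | 91.8 |
| Offsetting | 813 | 4.4 | 4.8 | 100 | 100 |
| Offsetting | 1355 | 4.9 | 4.7 | 100 | 100 |
| Uniform | 242 | 78.4 | 61.9 | 4.8 | 5.1 |
| Uniform | 813 | 99.9 | 98.0 | 5.2 | 4.6 |
| Uniform | 1355 | 100 | 100 | 5.2 | 4.8 |

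**Reading B: the tests compare baseline subgroups, pooled over arms.** With 1:1 allocation, the pooled difference = prognostic difference + ½ × difference in treatment effect.
- Offsetting effects, no prognostic difference: ½ × (0.5 − (−0.5)) = 0.5 SD, flagged in 100% of runs.
- Prognostic difference of 0.25 SD, no treatment effect at all: flagged in 78.9%, 99.9% and 100% at 242, 813 and 1355 per arm.

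The test responds to both and cannot tell them apart. The interaction test rejected in 4.3–5.3% (continuous) of the purely prognostic runs.

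**The latent step.** With no re-randomisation (800 people, four time points, well-separated classes, 200 runs), BIC chose two or more classes in 100% of two-class runs and 0% of homogeneous runs. As a method it can see differing trajectories.

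The window matters. Follow-up assessments are at months 1.5, 3, 6, 9, 12, 18, 24 and 30 (Clinical evaluators). First-line treatment ends at month 3 for IPT and month 6 for fluoxetine, so 6 of 8 and 5 of 8 assessments respectively fall after it.

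This was simulated with 1,000 people, eight visits, identical first-line response for all, and about half re-randomised after month 3:
- No second-line effect: two or more classes in 0% of 100 runs.
- Combination 0.8 SD and switch 0.3 SD: 100% using all visits, 0% using visits to month 3.
- Combination 0.5 SD and switch zero: 83% of 40 runs using all visits, 0% to month 3. This figure is fragile. A repeat with non-remission set by the month-3 score gave 84% of 25 runs. A repeat with non-remission drawn independently of the score gave 5% of 40 runs.

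**The case against.** Four points on the other side carry weight.

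1. **The groups are not stated.** A reader might infer that the tests compare arms and are therefore blind to heterogeneity. The documents do not say so. Under the subgroup reading the tests do react to differences in outcome. What stands is that neither reading isolates differential treatment effect.

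2. **The tests are only the first step.** A reader might infer that the whole heterogeneity analysis is unsound. The paragraph goes on to a method built to find differing trajectories, and Aim 3 plans moderators and Q-learning. Nothing says that the first step decides whether the second is run, or that it counts as evidence alone.

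3. **The window is not stated.** A reader might infer that the latent model runs to month 30. The protocol sets no window, and under Study visits and again under Assessment schedule and rationale it speaks of symptom trajectories during treatment, which could mean a window that closes before re-randomisation. The defect is the missing specification.

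4. **The comparison favours interaction tests.** The simulated effects cancel exactly, and the interaction test is given the true subgroup label. With a subgroup unrelated to the listed factors (±0.3 SD, an assumed 500 per arm), each of the five interaction tests proposed under the fix rejected in only 5–6% of runs, no better than the t test. Five unadjusted tests also carry their own false positives: 1 − 0.95⁵ = 22.6% if independent, and 25% in simulation. This stands, and the fix has to allow for it.

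**Conclusion.** The point holds in a limited form. The chi-squared and t tests are not tests of heterogeneity on either reading, and their groups and time point are undefined. Used between arms, they reject at about the alpha level under offsetting effects and in 62–100% of runs under a uniform effect. Used between pooled subgroups, they flag pure prognosis in 79–100%. These sizes rest on the assumed effect patterns and on 242 to 1355 per arm. The qualitative result does not, because it follows from what the tests compare.

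The latent step is suitable for describing trajectories, but its classes can reflect second-line treatment if later visits are included. How often depends strongly on assumptions: 5% to 100% of runs in the scenarios with a second-line effect, and 0% when restricted to visits up to month 3. Even with a clean window, latent classes describe patterns of outcome and do not by themselves show that the effect of one arm over the other varies.

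The analysis is exploratory and has no decision rule. The primary test and the sample size are unaffected.

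**What to change.** - **Replace the first-step tests** with treatment-by-baseline-factor interaction terms in the first-line model. Use a short pre-specified list already collected: delivery mode, sex, baseline BDI, baseline PCL, and baseline MDD only / PTSD only / both. Link this to Aim 3. In the SAP's model the treatment effect is itself time-by-group, so the term needed is time-by-group-by-factor. The diagnosis factor cannot be fitted that way for binary MDD under a log link, since PTSD-only participants have zero baseline risk. For that factor use the protocol's end-of-treatment logistic model or the continuous scores.
- **Control multiplicity** with one global interaction test or an adjustment across the list, and report the results as exploratory.
- **Fix the latent model's window** to first-line visits, noting that first-line treatment ends at month 3 for IPT and month 6 for fluoxetine, or include second-line assignment as a time-varying covariate. State that this step does not depend on the first, and describe its classes as outcome patterns, not treatment-effect subgroups.
- **Carry the analysis into the SAP.**

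The cost is protocol and SAP wording and modest extra analysis, with no new data. The downside is that interaction tests have less power than main-effect tests and can detect only heterogeneity related to the listed factors.

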used in 2 ongoing studies in Kisumu, Kenya.(Onu et al., n.d.) These are a mixed method study whose main objective is to identify the mental health impact of providing testimony to FIDA legal providers for women with claims related GBV and a capacity Building Randomized Controlled Trial of Interpersonal Psychotherapy for HIV+ Women Affected by Gender Based Violence. The studies are not formal psychometric evaluation/validation studies, but show acceptability and convergent validity. As the results of those measures were corroborated by qualitative assessments. The BDI also showed convergent validity in Luo (as well as the Kiswahili) with the MINI MDD diagnosis.

Table 1: SMART-DAPPER Measures	
Variable	Description
Demographics	Age, gender, marital status
Highest education	(1) None; (2) primary; (3) secondary; (4) tertiary and beyond
Individual income and employment, education, assets, school fees, and time allocation	Assessment of individual formal and informal income and employment, assets, education, and time allocation
Health co-morbidities	HIV, Malaria, HTN, DM
Proximity to clinic*	Location of residence relative to KCH and other Kisumu County Ministry of Health facilities
Overall challenges for attending depression care appointments at KCH and other Kisumu County Ministry of Health facilities, and by telephone and identification of top challenge*	(1) easy challenge (2) moderate challenge (3) difficult challenge (4) impossible or nearly impossible challenge; (5) Identify source of the greatest challenge in text (e.g., money, logistics, stigma, etc.)
Cost of transport from residence to KCH and other Kisumu County Ministry of Health facilities, and any associated telephone costs **	(1) 0-100KSH (2) 100-300KSH (3) 300-500KSH (4) more than 500KSH

Opportunity costs per depression treatment session: lost wages, dependent care**	(1) 0-100KSH (2) 100-300KSH (3) 300-500KSH (4) more than 500KSH
Major Depressive Disorder (MDD)	Beck Depression Scale (BDI)(Beck, Ward, Mendelson, Mock, & Erbaugh, 1961), MINI MDD module (D V Sheehan, 1998)
Post-traumatic Stress Disorder (PTSD)	Posttraumatic Stress Checklist (PCL-5), MINI PTSD module (D V Sheehan, 1998), Primary Care PTSD Screen for DSM-5 (PC-PTSD-5) (Prins A, 2015)

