Acceptability and Appropriateness. Interview material will be recorded in audio files, transcribed and translated. Dedoose software will be used to analyze the resulting text using grounded theory. Grounded theory sorts data in three ways: through concepts, categories and propositions. Concepts are identified by seeking conceptual similarities among focus groups/interviews. These concepts are grouped to develop categories of concepts. Categories are then compared and grouped to develop propositions or theoretical constructs about the phenomena of interest. Dedoose software facilitates coding of observations to work toward the theoretical construct. Data will be collected using a “triangulation” technique that compares information from various sources (focus groups, individual interviews) in order to increase the reliability and validity of the findings. ***Feasibility and Fidelity.*** Feasibility and fidelity measures will be assessed by sample means and proportions, with 95% confidence intervals, and compared to pre-specified benchmarks (above).

Service delivery mechanism: availability and affordability. *Hypothesis 1c* will be addressed by calculating RE-AIM for IPT and fluoxetine according to the procedures outlined in Glasgow et al.(Glasgow, Vogt, & Boles, 1999) Then, we will then evaluate how RE-AIM scores correlate with availability and affordability measures (Table 2) for IPT versus fluoxetine. Finally, we will evaluate for mediation by treatment completion. Specifically, we will begin with logistical regression models of RE-AIM score including availability factors and affordability factors. If any significant relationships exist, we will construct figures of hypothetical relationships between variables that are significantly associated with RE-AIM score and create path diagrams, using effect sizes to identify potential causal pathways between availability, affordability and RE-AIM scores for IPT versus fluoxetine.

Table 2: Calculating RE-AIM from an Effectiveness-Implementation Hybrid Type I (SMART-DAPPER)(Farris, Will, Khavjou, & Finkelstein, 2007; Glasgow, Klesges, Dzewaltowski, Estabrooks, & Vogt, 2006)

1	Reach will be calculated as the ratio of study participants who are eligible for SMART-DAPPER compared with those who choose to participate. Reach is the first assessment of RE-AIM.
Effectiveness Outcomes	
2a	MDD and/or PTSD remission from IPT or fluoxetine at month 3 (IPT) and month 6 (fluoxetine).

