2b	MDD and/or PTSD remission at month 1.5 (treatment mid-point) for IPT and at 3 months (treatment mid-point) for fluoxetine to identify the proportion of treatment gain achieved at mid-point compared with end of treatment (month 3). Treatment Effectiveness is a key aspect of RE-AIM.
3	Maintenance of month-3 remissions from IPT or and month 6 remissions from fluoxetine at follow-up assessments (months 6 (for IPT), 9, 12, 18, 24 and 30). Maintenance of gains is an individual level measure of Maintenance in RE-AIM.
Implementation Outcomes	
4	Both IPT and fluoxetine will be acceptable treatments for delivery in primary care as determined by qualitative interviews.
5	Both IPT and fluoxetine will be appropriate treatments for delivery in primary care as determined by qualitative interviews.

- 6 Both IPT and fluoxetine will be feasible treatments as determined by completion rates. *With the exception of those who leave the study because their symptoms remit, completion rate will be used as an individual level measure of Adoption in RE-AIM.*
- 7 Both IPT and fluoxetine will have strong treatment fidelity as determined by protocol adherence to IPT and fluoxetine administration. *Fidelity is a key component of Implementation in RE-AIM.*

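### The planned mediation analysis uses treatment completion as mediator of a RE-AIM score that counts completion as its Adoption component, so part of any indirect effect is built in

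*Protocol*

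**What the plan says.** The Protocol section on service delivery (availability and affordability) addresses a Hypothesis 1c in four steps.

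- **Score.** RE-AIM is obtained by "calculating RE-AIM for IPT and fluoxetine according to the procedures outlined in" a cited paper. No formula is printed.
- **Mediator.** "Finally, we will evaluate for mediation by treatment completion".
- **Model.** "Specifically, we will begin with logistical regression models of RE-AIM score including availability factors and affordability factors".
- **Pathways.** "If any significant relationships exist, we will construct figures of hypothetical relationships between variables that are significantly associated with RE-AIM score". Path diagrams are then drawn, "using effect sizes to identify potential causal pathways between availability, affordability and RE-AIM scores for IPT versus fluoxetine".

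Table 2 in the same section lists what goes into RE-AIM. Row 2a is remission at the end of first-line treatment, row 3 is maintenance of remission, row 6 is completion and row 7 is fidelity. Row 6 says that "completion rate will be used as an individual level measure of Adoption in RE-AIM". It sets one group apart, in these words: "With the exception of those who leave the study because their symptoms remit".

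Nothing in the Protocol removes Adoption from the score for the mediation step. The SAP does not mention this analysis.

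**The concern.** A mediation analysis asks whether the exposure (cost, access) changes the mediator (completion) and whether the mediator then changes the outcome. Here the mediator is also a component of the outcome. The second link is therefore guaranteed, and the analysis largely reduces to asking whether cost is related to completion.

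The Protocol expects that relation. Its Feasibility paragraph lists lost wages and the cost or burden of transport among the reasons for attrition. Hypothesis 3a expects time and cost of transport to weaken IPT relative to fluoxetine because IPT needs more visits. If cost lowers completion more under IPT, the built-in path will also differ between arms, and the plan intends to compare pathways for IPT versus fluoxetine.

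At stake is the reading of the result. A finding that costlier travel lowers attendance could be reported as a causal pathway to treatment results.

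**Working it through.** The plan states no figure for this analysis, so there is none to reproduce.

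**Inputs from the Protocol.** There are 2,710 participants, or 1,355 per first-line arm at 1:1. Average completion is 80%, from the 20% drop-out under Retention. Remission is 50%, from the sample size section. Table 1 gives four ordered cost bands. Two-sided alpha is 0.05, which the Protocol states only for the sample size.

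**Assumptions.** The bands are equally frequent. Maintenance is 60% of remitters and fidelity is 80%. The score is an equal-weight sum S = C + R + M + F (completion, remission, maintenance, fidelity), with a dichotomised sum (at least 3 of 4) and a product as alternatives. Mediation is declared when cost-to-completion and completion-to-score given cost are both p < 0.05. In truth, completion affects none of R, M or F.

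**Step 1: the built-in path.** For the sum, E[S | C=1, cost] − E[S | C=0, cost] = 1 + 0 + 0 + 0 = 1. If completion falls from 85% to 75% across the bands, the indirect effect is −0.10 × 1 = −0.10. That is simply the change in completion. With C removed from the score the path is 0 and the indirect effect is −0.10 × 0 = 0.

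**Step 2: cost to completion.** The slope per band is 0.10/3 = 0.0333 in size. With bands coded 0 to 3 (variance 1.25) and N = 2,710, the standard error is √0.16/√(2,710 × 1.25) = 0.4/58.2 = 0.0069. So z = 4.85 and power is over 99%. At N = 1,355, z = 3.43 and power is 93%.

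**Step 3: the plan's entry condition.** Path diagrams follow only if a factor is significantly related to the score. The variance of S is 0.16 + (0.25 + 0.21 + 2 × 0.15) + 0.16 = 1.08, so the SD is 1.04. At N = 2,710 the standard error of the cost-score slope is 1.04/58.2 = 0.0179, z = 0.0333/0.0179 = 1.87 and power is 46%. At N = 1,355, z = 1.32 and power is 26%.

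**Step 4: simulation, 600 runs per setting.** With completion in the score, the completion-to-score path was significant in 100% of runs under all three scorings. False mediation was declared as follows. The gated columns' ranges run across the three scorings.

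| Completion across bands | N=1,355, condition ignored | N=1,355, condition applied | N=2,710, condition ignored | N=2,710, condition applied |
|---|---|---|---|---|
| 82.5% to 77.5% | 39% | 3–6% | 71% | 6–13% |
| 85% to 75% | 94% | 9–26% | 100% | 15–48% |
| 90% to 70% | 100% | 26–78% | 100% | 38–96% |

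The hand calculations for the sum (46% and 26%) agree with the simulated 48% and 26%. A second setting, with completion falling from 80% to 69% and the condition applied, gave about 49% (sum) and 12% (dichotomised) at N = 2,710, and about 28% and 6% at N = 1,355. With remission alone as outcome (85% to 75%, N = 2,710), the rate was 4.8% with the condition ignored.

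**Step 5: row 6's exception.** Changing the outcome is not enough if remitted non-completers are set aside. Start with 542 non-completers (20% of 2,710), half of them remitted.

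- Set aside 20% of the remitted ones: remission among those kept is 0.40/0.90 = 44.4%, against 50% in completers. The difference is 5.6 points, SE = √(0.25/2,168 + 0.247/488) = 0.025, z = 2.23 and power is about 61%.
- Set aside 50%: 0.25/0.75 = 33.3%, a difference of 16.7 points and z = 6.5.

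Simulated false mediation on remission was 62% and 98.5%, with the condition ignored.

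**The case against.** Several points on the other side are sound.

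- **No test is specified.** The plan names no mediation test or decision rule, and its wording (hypothetical relationships, potential pathways) is exploratory. A reader might infer that the trial will declare mediation whenever cost affects completion. The documents do not support that: the percentages rest on an assumed rule, and the frequency depends on power and on the plan's entry condition, which cuts it sharply.
- **The score is undefined.** The formula is given only by citation, and the text uses both score and scores. If the dimensions are analysed separately, only the Adoption model is circular. Logistic regression suggests a dichotomised score, which gives the lower end of each gated range. A participant-level fidelity value is also doubtful, since fluoxetine fidelity is audited on 10 charts a month.
- **RE-AIM may itself be the target.** The plan asks about pathways to RE-AIM scores, and Adoption belongs there by design. On that reading a contribution through completion is legitimate, but it is an accounting identity and does not show that completing treatment improves results.
- **Its standing is minor.** Hypothesis 1c is not among the hypotheses listed under Hypothesis and Specific Aims. Hypothesis 3a, on transport time and cost, uses remission and has no such overlap.

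The entry condition does not remove the problem, because completion also feeds the score used in that condition.

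**Conclusion.** The overlap is in the text: completion is the mediator and also the Adoption component of the outcome. If the score includes Adoption, or for the Adoption dimension if dimensions are analysed separately, a completion-to-score path is guaranteed. An indirect effect of cost or access can then appear with no clinical effect of completion.

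The size is conditional. With joint significance, 2,710 participants and a fall in completion of about 10 points, false mediation is near 100% ignoring the entry condition and roughly 12% to 50% applying it. The comparison is about 5% for remission alone, ignoring the condition and with no participant set aside. The near-100% figure should not be read as the error rate of the written procedure.

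A reader might also infer that the trial's main results are compromised. They are not: the SAP's primary and secondary outcomes do not use this score. The point should be corrected, but it concerns a secondary implementation analysis.

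**What to change.** State in the Protocol or SAP that:

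1. The mediation analysis uses outcomes that exclude Adoption and completion: end-of-treatment remission (Table 2, row 2a) and, separately, maintenance (row 3). Completion is the mediator, with adjustment for baseline BDI and PCL, sex and delivery mode.
2. All participants are kept in this analysis. Completion is defined by sessions attended, independently of remission status, so row 6's exception is not applied here.
3. The RE-AIM score formula, any cut-off for the logistic model and the mediation rule are written out.
4. Completion stays in RE-AIM for the descriptive summary only.

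This is a short wording change with no new data. Its downside is that the mediation result will be positive less often. One limitation remains and should be acknowledged: if early remission leads some participants to stop attending, remission influences completion, and keeping everyone in the analysis does not remove that reverse link.
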